### 6.2.1.1 PrEP Comparison Component Maternal Enrollment Visit

For eligible women, enrollment must occur in time for study drug initiation prior to 32 completed weeks of gestation. The point of enrollment is taken to be the time when a participant has successfully been entered in the Subject Enrollment System (SES). All Entry Visit procedures are expected to be performed on the day of enrollment; procedures that may provide information relevant to eligibility for the study (e.g., rapid HIV test, medical history, physical examination), should be performed first prior to final eligibility determination and assignment to a study cohort. If a participant is found to be ineligible on the day of enrollment, enrollment should not occur.

Additional requirements for sequencing of procedures at the Entry Visit are as follows:

- Rapid HIV testing, and final eligibility determination and confirmation must precede enrollment.
- For women in Cohort 1:
  - Enrollment must precede prescribing of study drug.
  - Study drug prescribing must precede dispensing.
  - Blood collection for baseline TFV-DP drug level evaluation must precede ingestion of study drug.

PrEP Comparison Component Maternal Enrollment Visit Procedures (Day 0)	
Administrative and Regulatory	

• Complete final eligibility determination and confirmation

• Complete eligibility checklist, enter checklist data into SES to enroll the participant, print and file a copy of the confirmation

• Collect comprehensive locator information

Behavioral and Counseling	

• iNSC [see Section 5.3.2 for specific counseling for each cohort]

• CASI and COVID-19 questionnaire [see Section 6.16]

Clinical	

• Update medication and medical history since last visit

• Perform complete maternal physical exam

Laboratory	
Collect blood for:
 

• HIV RNA test

• Store plasma for HIV drug resistance testing

• Rapid HIV test [see Section 6.3 in the event the test is (+)]

• Baseline TFV-DP level (DBS)

• Syphilis testing

• HSV2

 
Collect vaginal swab or urine for:
 

• Chlamydia and gonorrhea

 
Collect vaginal swab for:
 

• Microbiome

 
Collect rectal swab (if consented) for:
 

• Microbiome

Study Drug	
Cohort 1 only:
 

• Prescribe and dispense study drug

 A negative test result must be available prior to enrollment.

 Baseline sample must be collected prior to ingestion of study drug for Cohort 1 participants; the sample for Cohort 2 participants can be collected at any time and is required to confirm the participant is not receiving PrEP as standard of care.

## 6.2.1.2 PrEP Comparison Component Maternal Antepartum Week 4, 8, 12 (during pregnancy)

The Antepartum (AP) Week 4, 8 and 12 visits are targeted to take place on Study Days 28, 56 and 84 respectively, counted from the date of study entry as Day 0, with an allowable window of  $\pm 7$  days. A negative rapid HIV test result at each visit must be available, for participants in Cohort 1 and Cohort 2/Step 2, prior to prescribing study drug.

In addition to the standard of care HIV prevention package provided and routine safety evaluations for all study participants at these visits, adherence and acceptability assessments are performed in Cohort 1.

Participants in Cohort 1 and Cohort 2 may deliver prior to completion of the AP Week 8 or Week 12 visit. If so, evaluations indicated for the AP Week 8 and Week 12 visit should be conducted in addition to the evaluations required for the Maternal Labor and Delivery Visit (Week 0) ([Section 6.2.1.4](#)). In those cases, the visit window of the L&D visit (+14 days) will apply.

Note that women who are selected for and consent to participation in the Qualitative In-Depth Interview during pregnancy may be scheduled for their interview at or after the Week 12 visit. See [Section 6.2.1.8](#) for details about this visit.

PrEP Comparison Component Maternal AP Weeks 4, 8 and 12 ( $\pm 7$ days)		
Behavioral and Counseling		
 
CASI and COVID-19 questionnaire [see Section 6.16]
 
 
Week 12:
 
 
Qualitative IDI Visit [see Section 6.2.1.8]
 
 
Cohort 1 and Cohort 2/Step 2 only:
 
 
iNSC with drug level feedback [see Section 5.3.2]
 
 
Cohort 2 only:
 
 
iNSC [see Section 5.3.2]
 
Assess for social harms [see Section 13.6]
 

Clinical		
 
Obtain interim medical/medications history
 
Perform targeted physical exam
 
Identify/review/update adverse events
 
Perform additional evaluations per Section 8 and/or if clinically indicated (consult CMC if indicated)
 

Laboratory	Blood	
Collect blood for:
 
 
HIV RNA test
 
Store plasma for HIV drug resistance testing
 
Rapid HIV test [see Section 6.3 in the event the test is (+)]
 
 
Weeks 4, 12:
 
 
ALT, Creatinine, and CrCl
 
 
Cohort 1 and Cohort 2/Step 2 only:
 
 
TFV-DP level (DBS)
 

	Other	
Collect vaginal swab once at EGA 34-38/40 weeks for:
 
 
Microbiome
 
 
Collect rectal swabs once at EGA 34-38/40 weeks (if consented) for:
 
 
Microbiome
 
 
Cohort 1 and Cohort 2/Step 2 only; collect at one visit at EGA 34-38/40 weeks:
 
 
Collect vaginal secretions for drug level
 

Study Drug		
Cohort 1 and Cohort 2/Step 2 only:
 
 
Prescribe and dispense study drug
 

### 6.2.1.3 PrEP Comparison Component Maternal Antepartum Week 24 and 36

Participants in both Cohort 1 and Cohort 2 who enroll early in gestation (i.e., prior to 20 weeks' gestation) may return for visits at AP Study Weeks 24 and 36. These visits are targeted to take place 168 and 252 days from the date of study entry (Day 0), respectively, with an allowable window of  $\pm$  14 days.

In addition to the standard of care HIV prevention package provided and routine safety evaluations for all study participants at these visits, assessments are conducted in the PrEP study cohort of PrEP acceptability and adherence.

Note that women who are selected for and consent to participation in the Qualitative In-Depth Interview during pregnancy may be scheduled for their interview at the time of their regular study visit at Week 24 or 36 or at an alternative date. See [Section 6.2.1.8](#) for details about this visit.

PrEP Comparison Component Maternal AP Week 24 and 36 Visit Procedures ( $\pm$ 14 days)	
Administrative and Regulatory	
 
Review locator information
 

Behavioral and Counseling	
 
CASI and COVID-19 questionnaire [see Section 6.16]
 
Qualitative IDI Visit: [see Section 6.2.1.8]
 
 
Cohort 1 and Cohort 2/Step 2 only:
 
 
iNSC with drug level feedback [see Section 5.3.2]
 
 
Cohort 2 only:
 
 
iNSC [see Section 5.3.2]
 
Assess for social harms [see Section 13.6]
 

Clinical	
 
Obtain interim medical/medications history
 
Perform targeted physical exam
 
Identify/review/update adverse events
 
Perform additional evaluations per Section 8 and/or if clinically indicated (consult CMC team if indicated)
 

Laboratory	
Collect blood for:
 
 
HIV RNA test
 
Store plasma for HIV drug resistance testing
 
Rapid HIV test [see Section 6.3 in the event the test is (+)]
 
ALT, Creatinine, and CrCl
 
 
Cohort 1 and Cohort 2/Step 2 only:
 
 
TFV-DP level (DBS)
 

	
Collect vaginal swab once at EGA 34-38/40 weeks for:
 
 
Microbiome
 
 
Collect rectal swabs once at EGA 34-38/40 weeks (if consented) for:
 
 
Microbiome
 
 
Cohort 1 and Cohort 2/Step 2 only; collect once at EGA 34-38/40 weeks:
 
 
Collect vaginal secretions for drug level
 

Study Product	
Cohort 1 and Cohort 2/Step 2 only:
 
 
Prescribe and dispense study drug
 

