#### 6.2.1.4 PrEP Comparison Component Maternal Labor and Delivery Visit

*Note: The calendar will reset after delivery for postpartum visits, with the delivery date considered as Day 0, and subsequent visits calculated from this date.*

The maternal labor and delivery visit will be conducted within 14 days of delivery. If the delivery visit is conducted within 30 days of the last visit, procedures do not need to be repeated except for the rapid HIV test, HIV RNA test and plasma storage for future resistance testing. If the mother does not deliver a live born infant the mother should still complete the Delivery Visit and all subsequent postpartum visits if she is willing to do so.

PrEP Comparison Component Maternal Labor and Delivery Visit Procedures (L/D +14 days)	
Administrative and Regulatory	

Review locator information

Behavioral and Counseling	

Qualitative Interview IDI Visit: to take place at the L/D visit or at an alternative date [see Section 6.2.1.8]

 
Cohort 1 and Cohort 2/Step 2 only:
 

iNSC with drug level feedback [see Section 5.3.2]

 
Cohort 2 only:
 

iNSC [see Section 5.3.2]

Assess for social harms [see Section 13.6]

Clinical	

Obtain interim medical/medications history, including pregnancy outcome

Perform targeted physical exam

Identify/review/update adverse events

Perform additional evaluations per Section 8 and/or if clinically indicated (consult CMC if indicated)

Laboratory	Blood 
Collect blood for:
 

HIV RNA test

Store plasma for HIV drug resistance testing

Rapid HIV test [see Section 6.3 in the event the test is (+)]

TFV- DP level (DBS)

ALT, Creatinine, and CrCl

Other	Radiology 
DXA scan of:
 

Hip

Lumbar Spine

Study Product	
Cohort 1 and Cohort 2/Step 2 only:	

Prescribe and dispense study drug

	

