### **9.3.2 Participant Safety**

On behalf of the Protocol Team, the CMC will closely monitor participant safety through routine review of safety data reports generated by the SDMC. These reports will provide tabulations of adverse events (defined in [Section 8.1](#)) and social harms (refer to [Sections 7.2](#) and [13.6](#)) identified in enrolled participants, including abnormal laboratory test results, signs, symptoms, and diagnoses, pooled across arms. Further detail will be provided in the SPDSMP. The CMC will review these reports via conference call or other meeting at least monthly. Prior to each call, the DAIDS Medical Officer will review any AEs  $\geq$ Grade 3 and EAEs (defined in [Section 7.3](#)) reported to the DAIDS Safety Office that are not yet reflected in the data reports. The CMC will continually evaluate the pattern and frequency of reported events and assess for any individual occurrences or trends of concern.

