### **13.6 Potential Social Impact**

Participation in clinical research includes the risk of loss of confidentiality. Although study sites make every effort to protect participant privacy and confidentiality, it is possible that participants' involvement in the study could become known to others, and that social harms – non-medical adverse consequences – may result (e.g., because participants could be perceived as being HIV-infected or at "high risk" for HIV infection, or because a participant's choice to participate or use PrEP is not supported). For example, participants could be treated unfairly, or could have problems being accepted by their families and/or communities or could experience problems in their relationships with their partner(s). The Protocol Team believes this risk is small, given that the target population is HIV-uninfected women; however, study staff will work to minimize such potential risks both at the clinic and community levels.

At every follow-up visit in the PrEP Comparison Component, sites will assess for social harms experienced since the last visit. All reported social harms will be source documented and entered into eCRFs for maternal participants. As part of routine study monitoring, social harms will be tabulated and reviewed as described in [Sections 7.2](#) and [9.3.2](#). In the event that a participant reports a social harm, every effort will be made by study staff to provide appropriate follow-up support and counseling to the participant as necessary; referrals to appropriate non-study resources may also be provided. Each site will provide such support in accordance with local standards of care and site SOPs.

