 If the participant has not delivered at 12 weeks of follow-up, participants may choose to continue in follow-up until delivery, refer to [Section 5.1.2.1](#)

 If within the window of one of the weekly visits, visits may be combined.

 Questionnaire is done at Week 12 visit only; questionnaire is not required at early D/C.

 If positive refer to [Section 6.3](#) and [Appendix IID](#) for additional procedures.

 Store plasma for HIV drug resistance testing at all visits indicated EXCEPT Screening.

 Blood collected for other tests will be used for the rapid HIV test. Collection of additional blood is not required.

 Urine (5mL) or blood (1mL) tests are acceptable. The total blood volume shown above accommodates collection of 1mL of blood, if needed.

## Appendix IB (Schedule of Evaluations): Infant PK Component Group 1

INFANT PROCEDURES: Group 1	Birth	PP Wk 6	Early D/C
Medical and Medications History	X	X	X
Physical Examination	X	X	X
Infant Feeding History	X	X	X
LABORATORY EVALUATIONS			
Creatinine	1mL	1mL	1mL
TFV-DP level (DBS)	0.5mL		
Total maximum blood volume	1.5mL	1mL	1mL

## Appendix IC (Schedule of Evaluations): Infant PK Component Group 2

INFANT PROCEDURES: Group 2	Entry (Day 0)	Wk 6	Wk 12 and Early D/C
Medical and Medications History	X	X	X
Physical Examination	X	X	X
Infant Feeding History	X	X	X
LABORATORY EVALUATIONS			
Creatinine	1mL	1mL	1mL
TFV-DP level (DBS)	0.5mL	0.5mL	
Total maximum blood volume	1.5mL	1.5mL	1mL

## Appendix IIA (Schedule of Evaluations): Maternal PrEP Comparison Component: Cohort 1, Cohort 2/Step 2

MATERNAL PROCEDURES:	SCR	Entry	Wk 4	Wk 8	Wk 12	Wk 24	Wk 36	L&D	PP Wk 6	PP Wk 14	PP Wk 26 / Exit and Early D/C	Interim Visit
Informed Consent	X											
Medical and Drug History	X	X	X	X	X	X	X	X	X	X	X	
Physical Examination	X	X	X	X	X	X	X	X	X	X	X	
Study drug dispensing		X	X	X	X	X	X	X	X	X		
Assess for social harms			X	X	X	X	X	X	X	X	X	
iNSC	X	X										X
iNSC with drug level feedback			X	X	X	X	X	X	X	X		
CASI evaluations and COVID-19 questionnaire		X	X	X	X	X	X			X	X 	
Qualitative IDI							X				X	
HIV RNA  ; store plasma for HIV drug resistance testing 	4mL	6mL	6mL	6mL	6mL	6mL	6mL	6mL	6mL	6mL	6mL	
Rapid HIV 	X	X	X	X	X	X	X	X	X	X	X	
TFV-DP level (DBS)		4mL	4mL	4mL	4mL	4mL	4mL	4mL	4mL	4mL	4mL	
Complete Blood Count	3mL										3mL	

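### Five Section 6.2 visit tables restrict social-harm assessment to Cohort 2, contradicting Appendix IIA and Section 13.6, which require it for women on PrEP at the same visits

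*Protocol*

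**What the plan says.** Three parts of the protocol bear on the point.

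- **Section 6.2 visit tables.** The table for antepartum Weeks 4, 8 and 12 (6.2.1.2) reads "Cohort 2 only: iNSC [see Section 5.3.2 ] Assess for social harms". The parallel list for Cohort 1 and Cohort 2/Step 2 contains only counselling with drug-level feedback. The tables for antepartum Weeks 24 and 36 (6.2.1.3), Labor and Delivery (6.2.1.4), postpartum Week 6 (6.2.1.5) and postpartum Week 14 (6.2.1.6) have the same layout.
- **Appendix IIA.** This schedule is titled "Maternal PrEP Comparison Component: Cohort 1, Cohort 2/Step 2". Its row "Assess for social harms" is marked at nine columns: Weeks 4, 8, 12, 24 and 36, Labor and Delivery, and postpartum Weeks 6, 14 and 26 (the last shared with early discontinuation).
- **Section 13.6.** The rule is general: "At every follow-up visit in the PrEP Comparison Component, sites will assess for social harms experienced since the last visit". Among the sources of harm it lists is that harm may arise "because a participant's choice to participate or use PrEP is not supported".

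The postpartum Week 26 table (6.2.1.7), the maternal early discontinuation table (6.4.2.1) and both step-change tables (6.2.3.2) list the item with no cohort restriction.

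**The concern.** Section 13.6 names lack of support for a woman's decision to use PrEP as one route to social harm. Read literally, the five tables leave the item out for the women who are using PrEP and keep it for those who declined.

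The assessment is a participant-protection procedure in women aged 16 to 24. A reported harm leads to an eCRF entry, support and counselling, and possibly referral (13.6), and social harms are tabulated for the Clinical Management Committee's review at least monthly (9.3.2). If sites differ in which part of the protocol they work from, harms in women on PrEP may be recorded late or incompletely at some sites, while Cohort 2 is asked at every visit.

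**Working it through.** No formula applies. The check is a side-by-side reading of the visits at which women in Cohort 1 or Cohort 2/Step 2 are to be assessed.

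| Visit | Section 6.2 table | Appendix IIA | Section 13.6 |
|---|---|---|---|
| AP Week 4 | Cohort 2 list only | marked | required |
| AP Week 8 | Cohort 2 list only | marked | required |
| AP Week 12 | Cohort 2 list only | marked | required |
| AP Week 24 | Cohort 2 list only | marked | required |
| AP Week 36 | Cohort 2 list only | marked | required |
| Labor and Delivery | Cohort 2 list only | marked | required |
| PP Week 6 | Cohort 2 list only | marked | required |
| PP Week 14 | Cohort 2 list only | marked | required |
| PP Week 26 / early discontinuation | all women (6.2.1.7, 6.4.2.1) | marked | required |

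**Count.** Appendix IIA marks 9 columns. The tables disagree at 8 and agree at 1 (8 + 1 = 9). The 8 come from five tables: 3 + 2 + 1 + 1 + 1.

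**Could this be an artefact of text extraction?** A lost indent is possible in principle. But the placement repeats in five separate tables, while the Week 26, early discontinuation and step-change tables carry the item unrestricted. One stray indent would not produce that pattern.

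**Is there a rule that settles the conflict?** The opening of Section 6 sends the reader to Appendices I and II for the schedules and describes its own content as additional visit-specific information. The same opening treats the procedures listed in Section 6 as protocol-specified. Nothing says which prevails.

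**What follows if a site uses the tables?**
- Cohort 1: the first scheduled assessment is at postpartum Week 26 or early discontinuation.
- Cohort 2/Step 2: the woman is assessed at her earlier Cohort 2 visits and at both step-change visits. After that, Section 6.2.3.2 tells the site to apply the Cohort 1 procedures of Section 6 and Appendix IIA. Those two sources conflict; under the tables the assessment stops until Week 26 or early discontinuation.

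**What follows if a site uses Appendix IIA or 13.6?** Nothing is omitted.

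**The case against.** The best reply is that the intended rule is plain elsewhere. Appendix IIA is the schedule for women on PrEP, Section 13.6 has no cohort limit, and each affected bullet points to 13.6 ("Assess for social harms [see Section 13.6"). A site would have to overlook both its schedule and the section the bullet cites. This makes the consequence conditional, but it does not remove the contradiction: the tables are what staff are likely to have open at the visit, and they name a cohort explicitly.

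Other contacts also exist. Women on PrEP receive weekly two-way SMS with a staff call if a problem is reported or no reply comes (5.3.2). The computer-assisted interview covers PrEP stigma, disclosure and gender-based violence (6.16.2.2). Harms a woman volunteers are still documented (7.2). These lessen the risk, so it would be wrong to infer that women on PrEP go unasked about their circumstances until exit. They are not substitutes: the documents do not route interview answers to the social-harm eCRF, and the interview is not scheduled at Labor and Delivery or postpartum Week 6.

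Four stronger readings are tempting, and the documents do not support them.

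- *That all women on PrEP are first asked at Week 26.* This can hold only for Cohort 1. Step 2 women are asked earlier, as shown above.
- *That the omitted assessments can be counted by multiplying visits by the 233 women planned for Cohort 1.* That ignores the planned attrition of about 15% (9.2.4), early deliveries that merge visits (6.2.1.2), and the waiver of most repeat procedures when the delivery visit falls within 30 days of the last one (6.2.1.4). It also assumes that every site follows the tables. Few women can reach antepartum Week 36, which falls 252 days after entry.
- *That the gap would be hidden because Section 9.3.2 reports events "identified in enrolled participants, including abnormal laboratory test results, signs, symptoms, and diagnoses, pooled across arms".* Section 9.3.1 provides for review of data completeness, and the detail of the safety reports is left to a separate monitoring plan that is not among these documents.
- *That a planned cohort comparison is biased.* Social harms are not an outcome in protocol Tables 5 to 7 or in SAP Section 3.2.

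**Conclusion.** The contradiction stands. Five Section 6.2 tables conflict with Appendix IIA and Section 13.6 at eight of nine marked follow-up columns, and the protocol does not say which source governs. It is a drafting inconsistency, and nothing in the documents suggests that women on PrEP were left out on purpose.

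The consequence rests on one assumption: that at least some sites work from the Section 6 tables. At those sites a required assessment would be omitted in Cohort 1 before postpartum Week 26 or early discontinuation, and in Cohort 2 women between their step change and those visits. Social harms could be found late or under-recorded in women on PrEP relative to Cohort 2. How many assessments would be affected cannot be derived from the documents. No primary estimand, sample size or power figure changes. It should still be corrected, because the item exists to protect participants.

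**What to change.** In the tables of 6.2.1.2, 6.2.1.3, 6.2.1.4, 6.2.1.5 and 6.2.1.6, move the social-harm item out of the Cohort 2 list and place it with the procedures that apply to all maternal participants, as the Week 26 and early discontinuation tables already do. That brings the tables into line with Appendix IIA and Section 13.6.

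The cost is a clarification memo to sites and the same edit at the next amendment. No procedure, visit or data field is added, since the schedule and 13.6 already require the assessment. The analysis plan needs no change.

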#### 6.2.1.4 PrEP Comparison Component Maternal Labor and Delivery Visit

*Note: The calendar will reset after delivery for postpartum visits, with the delivery date considered as Day 0, and subsequent visits calculated from this date.*

The maternal labor and delivery visit will be conducted within 14 days of delivery. If the delivery visit is conducted within 30 days of the last visit, procedures do not need to be repeated except for the rapid HIV test, HIV RNA test and plasma storage for future resistance testing. If the mother does not deliver a live born infant the mother should still complete the Delivery Visit and all subsequent postpartum visits if she is willing to do so.

PrEP Comparison Component Maternal Labor and Delivery Visit Procedures (L/D +14 days)	
Administrative and Regulatory	

Review locator information

Behavioral and Counseling	

Qualitative Interview IDI Visit: to take place at the L/D visit or at an alternative date [see Section 6.2.1.8]

 
Cohort 1 and Cohort 2/Step 2 only:
 

iNSC with drug level feedback [see Section 5.3.2]

 
Cohort 2 only:
 

iNSC [see Section 5.3.2]

Assess for social harms [see Section 13.6]

Clinical	

Obtain interim medical/medications history, including pregnancy outcome

Perform targeted physical exam

Identify/review/update adverse events

Perform additional evaluations per Section 8 and/or if clinically indicated (consult CMC if indicated)

Laboratory	Blood 
Collect blood for:
 

HIV RNA test

Store plasma for HIV drug resistance testing

Rapid HIV test [see Section 6.3 in the event the test is (+)]

TFV- DP level (DBS)

ALT, Creatinine, and CrCl

Other	Radiology 
DXA scan of:
 

Hip

Lumbar Spine

Study Product	
Cohort 1 and Cohort 2/Step 2 only:	

Prescribe and dispense study drug

	

 DBS sampling is required for Cohort 1 and Cohort 2/Step 2 and Cohort 2; this requirement for Cohort 2 is to confirm and document the absence of PrEP exposure.

#### 6.2.1.5 PrEP Comparison Component Maternal Postpartum Week 6

The PP Week 6 visit will be conducted six weeks ( $\pm$  14 days) following the delivery date.

PrEP Comparison Component Maternal PP Week 6 Visit Procedures (Week 6 $\pm$ 14 days)	
Behavioral and Counseling	
Cohort 1 and Cohort 2/Step 2 only:
 

iNSC with drug level feedback [see Section 5.3.2]

 
Cohort 2 only:
 

iNSC [see Section 5.3.2]

Assess for social harms [see Section 13.6]

PrEP Comparison Component Maternal PP Week 6 Visit Procedures (Week 6 ± 14 days)			
Clinical		
 
• Obtain interim medical/medications history
 
• Perform targeted physical exam
 
• Identify/review/update adverse events
 
• Perform additional evaluations per Section 8 and/or if clinically indicated (consult CMC if indicated)
 
	
Laboratory	Blood	
Collect blood for:
 
 
• HIV RNA test
 
• Store plasma for HIV drug resistance testing
 
• Rapid HIV test [see Section 6.3 in the event the test is (+)]
 
 
Cohort 1 and Cohort 2/Step 2 only:
 
 
• TFV-DP level (DBS)
 
	
	Other	
Collect vaginal swab for:
 
 
• Microbiome
 
 
Collect rectal swabs (if consented) for:
 
 
• Microbiome
 
 
Cohort 1 and Cohort 2/Step 2 only:
 
 
• Collect vaginal secretions for drug level
 
	
Study Product		
Cohort 1 only and Cohort 2/Step 2 only:
 
 
• Prescribe and dispense study drug
 
	

#### 6.2.1.6 PrEP Comparison Component Maternal Postpartum Week 14

The PP Week 14 visit will be conducted 14 weeks (±14 days) following the date of delivery.

Women in Cohort 2 who have been selected for and consented to participate in the Qualitative Evaluations postpartum may undergo their in-depth interview at this visit or any time up to and including the PP Week 26 visit.

Because the DBS results from this visit will be used to evaluate adherence in Cohort 1, women from Cohort 1 may not be formally selected for participation in the Qualitative Evaluations until those results are available; however, if slots are still available study staff could approach potential participants to discuss the Qualitative Evaluations and to arrange for potential follow up for the in-depth interview, refer to [Section 6.2.1.8](#).

PrEP Comparison Component Maternal PP Week 14 Visit Procedures (± 14 days)	
Behavioral and Counseling	
 
• CASI and COVID-19 questionnaire [see Section 6.16]
 
• Qualitative IDI Visit [see Section 6.2.1.8]
 
 
Cohort 1 and Cohort 2/Step 2 only:
 
 
• iNSC with drug level feedback [see Section 5.3.2]
 
 
Cohort 2 only:
 
 
• iNSC [see Section 5.3.2]
 
• Assess for social harms [see Section 13.6]
 

Clinical	
 
• Obtain interim medical/medications history
 
• Perform targeted physical exam
 
• Identify/review/update adverse events
 
• Perform additional evaluations per Section 8 and/or if clinically indicated (consult CMC if indicated)
 

